#### *F.8.1 Request for Approval of Study Deviations*

The investigator shall obtain documented approval from Medtronic before implementation, for any change or deviation from the clinical investigation plan. In case of study deviations that can affect the subject's rights, safety or well-being or the scientific integrity of the clinical study, approval from the EC/IRB and regulatory authority must also be obtained before implementation. The investigator shall timely contact the Clinical Study Manager for review of the proposed change/deviation. Prior approval is not always realistic in situations where unforeseen circumstances are beyond the investigator's control. However, also in these cases, the event is considered a deviation, and shall be reported.

In any emergency situation the investigator shall exercise his/her judgment to safeguard the subject's interest. Such deviations from the clinical investigation plan do not require the prior approval of Medtronic. The investigator shall report the deviation as soon as possible to Medtronic and the reviewing EC/IRB, if applicable. Medtronic will inform the regulatory authorities, if required.

#### *F.8.2 Reporting Requirements for Study Deviations*

Medtronic is responsible for analyzing deviations, assessing their significance, and identifying any additional corrective and/or preventive actions (e.g. amend the CIP, additional training, terminate the study), such as those included in, but not limited to, the list below. Repetitive or serious investigator compliance issues may result in the need to initiate a corrective action plan, and in some cases freeze enrollment or ultimately terminate the investigator's participation in the clinical study:

- Non-compliance to obtain subject's informed consent
- Non-compliance to the inclusion/exclusion criteria
- Failure to follow subjects per scheduled follow-ups
- Failure to follow-up with findings on monitoring reports
- IRB/ EC approval expiration
- IRB/ EC suspension of the center

If a center is terminated or suspended, no additional enrollments will be allowed at the center. Unused investigational product allocated to the center will be returned to Medtronic.

Medtronic will provide site-specific reports to the investigators on a periodic basis summarizing information on deviations that occurred at the investigational site.

The investigator shall adhere to EC/IRB requirements and procedures for reporting study deviations.

#### *F.8.3 Amendments to the Clinical Investigation Plan*

The investigator can propose any appropriate modification(s) of the clinical investigation plan or investigational device or investigational device use. Medtronic will review this proposal and decide whether the modification(s) will be implemented.

Medtronic will submit any significant amendment to the clinical investigation plan, including a justification for this amendment, to the appropriate regulatory authorities and to the investigators to obtain approval from their EC/IRB. The investigator will only implement the amendment after approval of the EC/IRB, regulatory authority and Sponsor. Administrative amendments to the clinical investigation plan will be submitted to the EC/IRB for notification. Furthermore investigators shall sign any approved amendment of the clinical investigation plan, if required per local regulation.

## **G      QUALITY CONTROL PROCEDURES**

### **G.1    Procedures for database management**

#### *G.1.1    Data Collection*

The investigator must ensure accuracy, completeness and timeliness of the data reported in the eCRFs and in all other required reports. Data reported on the eCRFs which are derived from source documents must be consistent with the source documents and discrepancies need to be justified in a documented rationale, signed and dated by the principal investigator or co-investigator, and filed in the subject's medical file.

Only authorized persons can complete eCRFs. The investigator (physicians only) shall sign eCRFs as specified on the Delegated Tasks List/ Delegation of Authority Form included in the Investigator Site File.

The Electronic Data Capture (EDC) system maintains an audit trail on entries, changes, or corrections in eCRFs. If a person is only authorized to complete eCRFs or to make changes to an already signed eCRF, the investigator shall re-sign this eCRF.

Any source documentation as well as any imaging (e.g., procedure reports, imaging material, lab reports, death certificates, autopsy reports) that is sent to the sponsor should have all subject identifiers removed and replaced with the subject's study ID.

A paper copy of the eCRFs as well as access to the EDC system will be provided to the investigation site prior to subject enrollment.

#### *G.1.2    Source Data to be Directly Recorded on the Case Report Forms*

All data reported on the eCRFs shall be derived from source documents and be consistent with these source, and any discrepancies shall be explained in writing. There are no data that will be recorded directly on the eCRF without corroborating source documentation.

#### *G.1.3    Time Windows for Completion and Submission of Case Report Forms*

All data entry should be completed as soon as possible after the visit takes place. Adverse event and device deficiencies should be reported as described in the section F.6.

#### *G.1.4    Data Review and Processing*

Data management will be done according to Medtronic SOPs and the Data Management Plan for this clinical study. These documents will be made available on request.

All collected data will be reviewed for completeness, correctness and consistency. In case of issues, queries will be sent to the investigator or designee to complete, correct or comment the data.

## **G.2    Monitoring Procedures**

A site qualification visit may be conducted by Medtronic personnel (or designees) to review the clinical investigational plan and, regulatory and study requirements with the investigator and study personnel. A site initiation visit will be performed after it has been verified that the site is prepared for the study and that the site requirements for study participation are met.

On-site monitoring visits will be conducted at the start and during the clinical study in accordance with Medtronic SOPs and the Monitoring Plan. Frequency and timing of monitoring visits shall be determined by the Sponsor for each site based on enrollment rate and volume, study compliance and findings from previous visits.

It will be verified whether signed and dated informed consent forms have been obtained from each

subject before any clinical study related procedures are undertaken. Medtronic or designee will conduct site monitoring visits to monitor compliance with the protocol and adherence to the data collection procedures, to assess the accuracy and completeness of submitted clinical data, and to verify that records and documents are being properly maintained for the duration of the study.

In-person monitoring visits will be replaced by telephone and email contact to the sites by the study team. The sponsor monitoring phone calls will include an assessment of the source documents to assure completeness of image submissions and event reporting and an assessment of the essential documents. In particular, the focus of these calls will be to ensure that safety data is entered and to verify that all relevant events are reported. Site monitoring visits will be requested by the Sponsor if a concern arises with regards to compliance or data integrity.

#### ***G.2.1 Accessibility of Investigation Site Staff and Study Materials***

The principal investigator(s), his/her delegate(s), and the study coordinator(s) shall be accessible to Medtronic personnel or designee(s) and the Clinical Study Manager. This accessibility is of particular importance for reviewing data in the eCRF. Direct access to subject medical files for source data verification will need to be granted and prepared prior to any monitoring visits. If direct access cannot be provided per local laws and regulations, certified copies need to be made available or monitor needs to obtain access by reviewing alongside with study staff.

#### ***G.2.2 Audits and Investigation Site Inspections***

In addition to regular monitoring visits, Medtronic may conduct audits at participating investigational sites. The purpose of an audit is to verify the adequate performance of the clinical study related activities, independent of the employees involved in the clinical study. Regulatory bodies may also perform inspections at participating investigational sites. Any regulatory authority inspection announcements shall be forwarded immediately to the Clinical Study Manager.

The investigator and/or institution shall permit Medtronic and regulatory bodies direct access to source data and documents, taking into account any restrictions due to local law, to perform clinical study-related monitoring, audits, EC/IRB review, and regulatory inspections.

### **G.3 Study Suspension or Early Termination**

#### ***G.3.1 Early Study Suspension or Termination***

Medtronic or regulatory authority may decide to suspend or early terminate the clinical study (e.g. if information becomes available that the risk to study subject is higher than initially indicated, if interim analysis indicates that the results significantly differ from the study objectives or statistical endpoints). If the clinical study is terminated early or suspended, Medtronic shall promptly inform the investigators of the termination or suspension and the reason(s) for this. The investigator shall then promptly inform the reviewing EC/IRB and the study subjects.

#### ***G.3.2 Early Investigation Site Suspension or Termination***

Medtronic, EC/IRB, or regulatory authority may decide to suspend or prematurely terminate an investigation site (e.g. in case of expiring approval of the reviewing EC/IRB, non-compliance to the Clinical Investigation Plan or lack of enrollment).

If an investigation site is suspended or prematurely terminated:

- Medtronic shall promptly inform the clinical investigator(s) of the termination or suspension and the reason(s) for this
- The investigator shall then promptly inform the reviewing EC/IRB
- The investigator shall then promptly inform study subjects
- The investigator agreement will be terminated
- The investigator will inform the institution (where required by applicable regulatory requirements)

- Medtronic will inform the regulatory authority(ies) (where required by applicable regulatory requirements)

When the risks are found to outweigh the potential benefits or when there is conclusive proof of definite outcomes, investigators must assess whether to continue, modify or immediately stop the clinical study in the respective investigation site and immediately inform the sponsor and EC/IRB, if applicable.

#### **G.3.3 Subject Follow-up in Case of Termination**

If the study is terminated early, subjects will be followed as per routine standard of care by the investigational site or a treating physician which might be in line with the guidelines described in the *Management of Abdominal Aortic Aneurysms Clinical Practice Guidelines of the European Society for Vascular Surgery* or *Society for Vascular Surgery practice guidelines for the care of patients with an abdominal aortic aneurysm*.

### **G.4 Study Close Out**

Prior to completion of study close out, all data must be entered and approved in the EDC system. Medtronic and/or its designees will notify the site of the intention to close the study. Remote study close out visits may be performed. The intent of these visits will be to assuring that the investigator's regulatory files are up to date and complete and that any outstanding issues from previous visits have been resolved. Medtronic will notify and inform the site(s) that all requirements have been met with a study closure letter.

If required, EC/IRB and/or regulatory authority will be informed by Medtronic about the study close out.

## H DATA ANALYSIS AND REPORTING

Any deviations from this section will be described and justified in the final clinical study report, as appropriate.

### H.1 Analysis of Clinical Data

All observations will be analyzed descriptively. In general, qualitative parameters will be described by their distribution frequencies; quantitative parameters will be described by their mean, standard deviation, minimum, maximum, median, and number of subjects with assessable data.

The survival from all-cause mortality over one year time or longer will be described by the Kaplan-Meier survival curve and the associated Kaplan-Meier estimate will be calculated along with its standard error using the Greenwood method.

For events such as AEs, deaths and secondary procedures, that can occur or are observed at any time during the study, no time window will be applied. For such events, an event that occurs "within 1 month or 30 days" is an event that takes place between Days 0 to 30, inclusive. Similarly, an event that occurs "within 12 months or 365 days" is an event occurring between Day 0 to Day 365, inclusive. Date of event onset will be used to determine when the event occurred. Day 0 is referring to the day of index procedure.

For image-based assessments, such as stent-graft endoleak, patency, and other observations, the following time windows will be applied for by-visit data summaries:

**Table H-1: Time Windows for Statistical Analyses**

Study Visit	Target Day	Time Window
Implant	Day 0	Day 0
1 Month	Day 30	1 – 90 days
6 Months	Day 183	91 – 304 days
12 Months	Day 365	305 – 548 days
2 Year	Day 731	549 – 913 days
3 Year	Day 1096	914 – 1278 days
4 Year	Day 1461	1279 – 1644 days
5 Year	Day 1826	1645 – 2009 days

If there are two or more assessments in the same time window, then the assessment closest to the target day will be used in the analysis of event rate at a given timepoint.

In addition to endpoints, summaries of subject disposition, demographics, baseline characteristics, and subject accountability will be provided.

During statistical analysis, imputation of missing data will not be performed except for data related to the onset date of an adverse event or a death. In cases where the onset date of an event or a death is incomplete and unresolvable via data query, the 15th day of the known month or July 1st of the known year will be used.

Statistical analyses for this study will be performed using the Statistical Analysis System (SAS) for Windows (Version 9.1 or higher) or other widely-accepted statistical or graphical software.

**Statistical Hypothesis:**

The primary safety endpoint will be tested against a predetermined safety Performance Goal (PG) using the following statistical hypotheses:

$$H_0: p \geq 20\% \text{ vs. } H_1: p < 20\%$$

where  $p$  is the proportion of subjects experiencing a MAE within 30 days of the index procedure in the target population of subjects treated with the Endurant Evo AAA Stent graft system and 20% is the safety PG.

The primary effectiveness endpoint will be tested against a predetermined effectiveness PG using following statistical hypotheses:

$$H_0: q \leq 80\% \text{ vs. } H_1: q > 80\%$$

where  $q$  is the proportion of subjects who have a successful aneurysm treatment in the target population of subjects treated with the Endurant Evo AAA Stent graft system and 80% is the effectiveness PG.

If the null hypothesis ( $H_0$ ) is rejected at the one-sided 0.025 statistical significance level, it is considered that the PG for the associated endpoint has been reached.

Both safety and effectiveness endpoints are dichotomous study outcomes; hence, an exact method based on the binomial distribution will be used for the hypothesis testing.

Subset analyses by-sex, by-race (based on subjects enrolled in the US only, since collection of race and ethnicity data may not be allowed outside the US as per local law and regulation), and by-region/study site will be performed on the primary safety and effectiveness endpoints using descriptive statistics and reviewed for clinical significant difference. Sensitivity analysis using tipping point method may be performed, as needed, to assess the impact of missing data.

No inferential statistical analysis is planned for secondary or additional study endpoints. Descriptive statistics will be provided for all endpoints as well as baseline variables.

**Analysis Sets:**

The primary analysis set will consist of the Intent-to-Treat (ITT) population. This analysis set is defined as all subjects who were enrolled. Subjects will be considered as enrolled in the study as described in section F.1.

A secondary analysis set will be the Per-Protocol population. This analysis set is comprised of all ITT subjects who met inclusion and exclusion criteria, received the test device, and completed 12-month follow-up (including death but excluding withdrawal or lost to follow-up subjects within the 12-month follow-up period).

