**Enrollment:**

Those subjects who sign and date the informed consent document, meet all of the study eligibility criteria, and are approved by the IPR will be eligible for enrollment into the Endurant Evo US Clinical Trial. The subject will be considered to be enrolled when arterial access has been established with an attempt to introduce the Endurant Evo AAA stent graft.

Enrolled subjects will be documented on the Screening and Enrollment Log. Subjects who are enrolled, but not implanted with the device will be followed through the 1 month follow-up only.

The investigator will maintain a log of all subjects screened and enrolled in the clinical study, assigning an identification code linked to their names, alternative subject identification or contact information

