#### **F.2.1.2 Treatment Failure**

Inability to implant the Endurant Evo AAA stent graft system following arterial access due to deployment issues or entrapment of the delivery system will be considered a treatment failure. These subjects will be followed through the 1-month follow-up time point and then exited from the study.

If a primary conversion to open repair is required during the index procedure, then the subject will be followed for 1 month, at which time the subject will be exited from the study.

After exiting the study, subjects will be followed as per their institutional standard of care.

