#### **F.7.5 Conversion to Open Repair**

If a primary conversion to open repair is required during the index procedure, then the subject will be followed for 1 month, at which time the subject will be exited from the study.

If a secondary conversion to open repair is required during the follow-up period, then the subject will be followed for 30 days after the conversion, at which time the subject will be exited from the study.

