### 4.2. Secondary analysis set

A secondary analysis set will be the Per-Protocol population. This analysis set is comprised of all ITT subjects who met inclusion and exclusion criteria, received the test device, and completed 12- month follow-up (including death but excluding withdrawal or lost to follow-up subjects within the 12- month follow-up period).

 Results are from the Talent AAA (Talent AAA Control data referenced in Endurant Clinical Study Report, Appendix 2 of M090018\_M005 Clinical Module), Endurant (P100021) PMA 90-day update submission submitted via P100021/A002, and Endurant PMA supplement via P100021/S021. The results on successful aneurysm treatment are reported at 12 months and included all occlusions through the time period

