#### *Primary Effectiveness Endpoint*

The primary effectiveness endpoint is defined as the proportion of subjects with both technical success at the time of index procedure and treatment success at 12 months post-implantation. Successful aneurysm treatment is achieved based on the following criteria:

- Technical success at the index procedure (as assessed intra-operatively) is defined as successful delivery and deployment of the Endurant Evo AAA Stent graft system in the planned location and with no unintentional coverage of both internal iliac arteries or any visceral aortic branches and with successful removal of the delivery system

AND

- Treatment success consisting of freedom from:
  - AAA diameter increase, defined as  $> 5$  mm increase in maximum diameter as measured on CT scan (or MRA/MRI) at 12-month follow-up as compared to 1-month imaging
  - Types I and III endoleaks at 12-month follow-up including those requiring intervention through 12 months
  - Aneurysm rupture within 365 days
  - Conversion to surgery within 365 days
  - Stent graft migration resulting in a serious adverse event or requiring secondary intervention through 12 months

- o Stent graft occlusion through 12 months

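### The secondary Per-Protocol set removes never-implanted subjects and, on its natural reading, most converted subjects, so its effectiveness rate is biased upward

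*Protocol*

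**What the plan says.** Protocol H.1 and SAP 4.2 name two analysis sets.

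- **Primary set.** "The primary analysis set will consist of the Intent-to-Treat (ITT) population". Entry is at enrollment, and a subject is "enrolled when arterial access has been established with an attempt to introduce the Endurant Evo AAA stent graft" (Protocol F.1). A subject in whom implantation is attempted and fails is therefore in ITT.
- **Secondary set.** Per-Protocol is "all ITT subjects who met inclusion and exclusion criteria, received the test device, and completed 12-month follow-up". SAP 4.2 has the same conditions: "received the test device, and completed 12- month follow-up". Completion is qualified as "including death but excluding withdrawal or lost to follow-up subjects within the 12-month follow-up period".

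Three other provisions bear on this.

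- **Failure to implant.** Protocol F.2.1.2 classes inability to implant, because of deployment problems or an entrapped delivery system, as a treatment failure. It adds: "These subjects will be followed through the 1-month follow-up time point and then exited from the study".
- **Conversion to open repair.** A primary conversion leads to exit 1 month after the index procedure. After a later conversion the subject is "followed for 30 days after the conversion, at which time the subject will be exited from the study" (Protocol F.7.5).
- **Effectiveness endpoint.** It requires technical success at the index procedure and freedom from a list of events that includes "Conversion to surgery within 365 days" (SAP 5; the same in Protocol C.2.1.2).

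**The concern.** Two conditions for entering the Per-Protocol set depend on the effectiveness outcome. A subject who cannot be implanted has failed the endpoint and has not received the device. A subject converted at month 3 has failed the endpoint, exits about 30 days later, and so has no 12-month visit. In both cases the failure itself takes the subject out of the set.

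The one exception is for death, which is not a listed effectiveness component. The text therefore protects an early exit that is not a listed failure and is silent on one that is.

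The usual purpose of a second analysis set is to show whether the primary result is robust. A set that discards known failures and keeps successes cannot do that: agreement with ITT reassures less than it appears to, and a more favourable result may come from the definition alone.

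Safety has a related problem. One Per-Protocol set is defined, with no separate rule for the 30-day endpoint. As written, a subject with a MAE on Day 10 who withdraws at month 5, or who is later converted, drops out of any Per-Protocol safety analysis, although the 30-day outcome is fully known.

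**Working it through.** **1. The plan's own figure.** Protocol C.7 and H.1 give a goal of 80%, expected success of 90.5%, one-sided alpha of 0.025, an exact binomial test, 119 evaluable subjects and 90% power. At n=119 the exact rule is to pass with at least 104 successes. Its exact alpha is 0.0241 and its power at 90.5% is 0.901. With 15% attrition, 119/0.85 = 140. The stated effectiveness sample size reproduces.

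**2. Who leaves the set.**

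| Subject | In ITT? | Effectiveness failure? | In Per-Protocol? |
|---|---|---|---|
| Never implanted | Yes | Yes | No: device not received |
| Primary conversion (exit at 1 month) | Yes | Yes | No, on the natural reading |
| Secondary conversion, early or mid-year | Yes | Yes | No, on the natural reading: exits before the 12-month visit |
| Secondary conversion, late | Yes | Yes | Possibly yes |
| Graft deployed outside the planned location | Yes | Yes | Yes, if follow-up is completed |

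For the late conversions: the 12-month visit window opens on Day 335 (Protocol Table F-1) and exit is 30 days after conversion. A conversion on or after Day 335 − 30 = 305 could therefore still have a visit in the window.

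**3. Size of the bias.** Let N be the evaluable subjects, s the successes and k the failures removed. The rate moves from s/N to s/(N−k), a rise of s·k/[N(N−k)], which is never negative. The p-value is P(X ≥ s) for X binomial with 80% success. The documents give no counts, so s and k are assumptions. N=119 is the planned evaluable number. N=139 is actual global enrollment and so an upper limit.

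| N | s | s/N (p) | k | s/(N−k) (p) | Rise, points |
|---|---|---|---|---|---|
| 119 | 103 | 86.6% (0.042) | 1 | 87.3% (0.027) | 0.7 |
| 119 | 103 | 86.6% (0.042) | 2 | 88.0% (0.016) | 1.5 |
| 119 | 108 | 90.8% (0.001) | 1 | 91.5% (<0.001) | 0.8 |
| 119 | 108 | 90.8% (0.001) | 3 | 93.1% (<0.001) | 2.3 |
| 119 | 108 | 90.8% (0.001) | 5 | 94.7% (<0.001) | 4.0 |
| 139 | 120 | 86.3% (0.035) | 1 | 87.0% (0.022) | 0.6 |
| 139 | 126 | 90.6% (<0.001) | 5 | 94.0% (<0.001) | 3.4 |

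At N=119 each removed failure adds about 0.7 to 0.8 points (4.0/5 = 0.8 at k=5). Just below the cut-off, one or two removals carry the result across 0.025. Near the planned rate, both sets pass.

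**4. What the gap to ITT assumes.** The table treats the k subjects as failures in the ITT denominator. SAP Table 3 gives denominators for event rates and SAP Table 4 for imaging rates, but neither covers the composite. If exited subjects without a 12-month image also fell out of the ITT composite, the gap would shrink and the ITT rate would share the bias.

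**The case against.** The strongest reply is that nothing in the plan turns on this set. ITT is primary, study success is rejection of the two primary hypotheses, and no decision rule is attached to Per-Protocol. This stands. A reader might infer that a Per-Protocol pass could rescue an ITT failure, but neither document says so.

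A second reply is that removal of conversions is not stated. Only withdrawal and loss to follow-up are named as exclusions, Protocol F.7.1 lists conversion as a separate reason for exit, and a converted subject may be said to have completed all the follow-up required of them. This stands in part. A reader might infer that every conversion is removed by construction, and the text does not go that far. Exclusion is still the more natural reading, because death needed an explicit exception and conversion was given none. Two programmers could build two different sets.

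A third reply is that not all technical failures are lost. This is correct: misplaced or branch-covering grafts were received, and those subjects stay in.

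Fourth, excluding untreated subjects from a Per-Protocol set is a common convention. That is fair, and it is why the fix below does not insist on putting them back.

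On safety, a reader might cite a never-implanted subject with procedural blood loss of 1000 cc or more as a victim of the 12-month rule. That subject is removed by the device-receipt condition. The 12-month rule affects implanted subjects with an early MAE who exit later. The documents also do not say which endpoints will be analysed on the Per-Protocol set.

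**Conclusion.** The concern holds for the secondary set. The definition removes never-implanted subjects with certainty and most converted subjects on its natural reading. These are effectiveness failures, so the Per-Protocol success rate can be biased in one direction only, upward.

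The size is about 0.7 to 0.8 points per removed subject at about 119 evaluable: roughly 1 to 4 points for one to five such subjects, and enough to change the nominal test result only when the ITT count is just short of the cut-off. This rests on assumed counts and on ITT scoring these subjects as failures. The ITT primary conclusion does not change. The stronger statements, that all technical failures and all conversions are removed or that study success is at risk, are not supported.

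**What to change.** Amend SAP 4.2 and the Analysis Sets text in Protocol H.1:

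1. A subject who received the device and met any effectiveness failure component, including conversion, has a complete outcome and stays in the Per-Protocol set as a failure, whatever the later exit.
2. Twelve-month completion is required only of subjects without a failure.
3. Twelve-month completion is not a condition for the 30-day safety endpoint.
4. If never-implanted subjects remain excluded by convention, report their number beside the Per-Protocol rate and label that rate as conditional on implantation.

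Items 1 and 2 follow the logic the SAP already uses in Table 4, where the through-12-month denominator takes subjects with an event or with a readable 12-month image. A sentence in SAP 8.4 on how the same subjects count in the ITT composite would make the two rates comparable.

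The cost is wording; no new data are needed. The Per-Protocol rate becomes slightly less favourable. Keeping failures while dropping incomplete non-failures is itself mildly conservative, and the report should say so.
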